5.7.1.2 Pharmacokinetic Specimen Handling

The PK blood samples (5 mL each) will be collected into vacutainer tubes and allowed to clot blood at room temperature for at least 30 min (not exceeding 60 mins). Within 60 minutes of collection, the samples will be centrifuged for 15 minutes, at 2000 g, at 4°C, by a study team member.

The serum will be separated using a disposable plastic pipette and approximately equal volume of serum will be aliquoted in to two aliquots Aliquot A (primary) and Aliquot B (backup). The serum samples will be appropriately labeled and stored frozen at -80°C or below until shipment. Temperature monitoring logs should be maintained and accessible for review by the study monitor.

The Aliquot A samples (primary) will be shipped first, on dry ice, to the bioanalytical laboratory at FDA for processing when requested by the sponsor. The backup aliquot sample will be held for a further shipment, will be communicated by the sponsor. None of the PK blood samples will be stored for other analyses not specified in this protocol.

5.7.1.3 Pharmacokinetic Parameters

The following PK parameters will be determined for each subject:

- Maximum concentration (observed peak drug concentration) (C_{max})
- Time at which C_{max} occurs (T_{max})
- AUC from time 0 to the sampling time corresponding to the last quantifiable concentration (C_{last}) (AUC_{0-t})
- Elimination rate constant (K_{el})
- Terminal half-life ($t_{1/2}$)

- AUC from time 0 extrapolated to infinity (AUC_{0-inf})

5.7.2 Pharmacodynamic Assessments

5.7.2.1 Pharmacodynamic Sample Collection

5.7.2.1.1 Primary PD Biomarker

Blood samples (3.5 mL) for primary pharmacodynamic biomarker (peripheral blood eosinophils) assessment will be collected at the following time points:

- Day -1 (check-in)
- Day 1: 0 (pre-dose), 24 h
- Day 2, 3, 4, 5, 6, 7, 8, 9, 10, 11, 12, 13, 14, 21, 28, 35, 42, 49, 56, 63, 93, and 123

Blood samples will be collected by direct venipuncture or by inserting an IV catheter into the subject's forearm region. Each blood sample will be labeled with subject number, study number, study day, time point, event, and a barcode that matches that belonging to the subject.

5.7.2.1.2 Exploratory PD Biomarkers

Exploratory PD biomarkers will be evaluated using plasma proteomics and small RNA transcriptomics. Whole blood samples (6 mL) will be collected at the following time points:

- Day -1 (check-in)
- Day 1: 0 (pre-dose), 0.5, 1, 2, 3, 4, 6, 9, 12, 18, 24 h
- Day 2, 3, 4, 5, 6, 7, 8, 9, 10, 11, 12, 13, 14, 21, 28, 35, 42, 49, 56, 63, 93, 123

Blood samples will be collected by direct venipuncture or by inserting an IV catheter into the subject's forearm region. Each blood sample will be labeled with subject number, study number, study day, time point, event, and a barcode that matches that belonging to the subject. All blood samples will be processed for preparation of plasma.

5.7.2.2 Pharmacodynamic Specimen Handling

5.7.2.2.1 Primary PD Biomarker

Blood samples for primary pharmacodynamic biomarker (peripheral blood eosinophils) assessment will be collected at each time-point specified (Table 9-1). Samples will be processed and transported to Covance according to the SOP for flow cytometry samples.

5.7.2.2.2 Exploratory PD Biomarkers

Whole-blood samples will be collected at each time-point specified (Table 9-1). Approximately 5 mL per patient will be collected and processed to provide plasma for proteomics and small-RNA transcriptomics.

Whole blood should be collected in BD Vacutainer® Venous Blood Collection Tubes containing EDTA (or any other primary blood collection tube containing EDTA as anticoagulant) and stored at room temperature (15–25°C) or 4°C before processing within 1 hour. Heparin-containing blood collection tubes should not be used as this anticoagulant can interfere with downstream analyses.

Plasma samples should be processed, aliquoted (approximately 500 μ L volumes), and placed into the -80C freezer within 2 hours of collection.

5.7.2.3 Pharmacodynamic Parameters

5.7.2.3.1 Primary PD Biomarker

The following PD parameters will be determined for each subject:

- AUEC from Baseline to the sampling time corresponding to the return to Baseline (AUEC_{0-t})
- Percentage area under the effect curve (pAUEC) change from baseline truncated after return to baseline
- Maximum effect (greatest reduction of blood eosinophils observed) (E_{max})

5.7.2.3.2 Exploratory PD Biomarkers

Plasma proteome and small RNA transcriptome: Circulating proteins and small RNAs across ten or more specific time-points (to allow modeling of AUEC) and multiple drug doses will be evaluated using a systematic approach to discovery and replication of PD biomarkers and/or hypothesis-generation. Differential expression analysis (as well as candidate pathway analyses) of proteomic and small RNA data will be performed, respectively, at specified time points in the higher dose groups (discovery phase). Any promising PD biomarkers or patterns identified in this phase will then be independently and technically evaluated for differential expression in the remaining intermediate and low dose groups (replication and technical validation phase).

5.7.3 Additional Assessments

5.7.3.1 Sample Collection

Samples for genomic or other omic biomarker assessment will be collected at the following time points:

- Buffy coat: Day 1 (Pre-dose)

- Urine Sample Collection: Screening, Day -1 (check-in), Day 1 (Pre-dose and 24 hours), and Days 7, 28, 63, and 123

These samples will be used for analyses that will be considered hypothesis-generating and exploratory. All sample analysis will be performed by DARS staff.

5.7.3.2 Specimen Handling

A buffy coat from each study participant will be used for exploratory genomic analyses. On the specified collection day/time (Day 1, pre-dose), 5 mL of whole blood sample will be processed for plasma and the upper plasma phase will be transferred to a new sterile Falcon tube without disturbing the intermediate buffy coat layer. The buffy coat layer will then be transferred to a sterile 2 mL Eppendorf (safe-lock) tube (on wet ice). Buffy coat samples should be immediately frozen in a dry ice/ethanol bath (for ~ 40 seconds) and then transferred to a -80°C freezer. Only sterile (nuclease-free) plastic pipettes, pipette tips and tubes should be used. All barcoded buffy coat Eppendorf tubes should be frozen and stored at -80°C as described above until appropriately transported to the FDA for long-term storage. Sample analysis will be performed by DARS research staff.

At specified times for urine sample collection, 3-5 mL of urine will be processed according to the SOP, separated into 6 approximately equal aliquots, immediately frozen in a dry ice/ethanol bath (for ~40 second or until frozen), and then immediately transferred to -80°C for long-term storage. Sample analysis will be performed by DARS staff.

5.7.4 Safety Assessments

Safety will be evaluated in terms of AEs, clinical laboratory results, vital sign measurements (blood pressure, heart rate, respiratory rate, and oral body temperature), safety 12-lead and telemetered ECG results, and physical examination findings.

5.7.4.1 Adverse Events

5.7.4.1.1 Adverse Event Definitions

An AE is defined as any untoward and/or unintended sign, including an abnormal clinical laboratory finding, symptom, or disease temporally associated with the use of a study drug, whether or not considered related to the study drug. Events or conditions that increase in frequency or severity during or as a consequence of use of a drug in human clinical trials will also be considered AEs.

A treatment-emergent adverse event (TEAE) is defined as an AE that begins after study drug administration.

An unexpected AE is any AE having a specificity or severity not consistent with the current investigator's brochure for the study drug(s).

A serious adverse event (SAE) is defined as any AE occurring at any dose that meets the following criteria:

- Results in death,
- Is life threatening,
- Requires hospitalization or prolongation of existing hospitalization,
- Results in persistent or significant disability or incapacity,
- Results in a congenital anomaly/birth defect due to exposure prior to conception or during pregnancy, or
- Is an important medical event that may not meet the previous criteria but, based upon appropriate medical judgment, jeopardizes the subject or requires medical or surgical intervention to prevent one of the outcomes listed previously.

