Pharmacodynamics: Peripheral Blood Eosinophils AUEC will be calculated for each subject. For each dose, separate intervals will be used for the AUEC assessment to truncate noise introduced from baseline fluctuations. Maximum decrease from baseline will be determined from all sampled timepoints. For both assessments and biomarkers, measures will be log-transformed and utilize an ANCOVA approach for calculating geometric means and 90% confidence intervals for each treatment.

Separate population PD analyses will be conducted using nonlinear mixed effect modeling with NONMEM. AUECs calculated for each subject from all doses for a drug and placebo patient will be combined and evaluated assuming a saturating E_{max} relationship to characterize system parameters such as E_{max} and EC_{50} .

Pharmacokinetics: C_{max} and AUC are the primary PK parameters of interest in PK similarity studies with a subcutaneous drug administration. These and additional PK parameters will be determined for each subject using non-compartmental methods. All parameters will be reported with standard descriptive statistics including the geometric mean and coefficient of variation. Calculation of PK parameters will be performed using actual sampling times.

Safety

The safety population will include all subjects who receive at least 1 dose of any of the study drugs. All AEs will be coded using the Medical Dictionary for Regulatory Activities (MedDRA). The incidence of AEs, organized by system organ class and preferred term, will be summarized with a focus on treatment-emergent AEs. Vital sign measurements will be summarized using descriptive statistics by time point. All values will be evaluated for clinically notable results. Data for additional safety parameters (e.g., physical examination findings) will be listed.

Date of Protocol: 25 June 2020

1. List of Abbreviations

Abbreviation	Definition
AE	adverse event
Ag/Ab	antigen/antibody
ANCOVA	analysis of covariance
AUC	area under the concentration-time curve
AUEC	area under the effect curve
pAUEC	percentage area under the effect curve
CFR	Code of Federal Regulations
CHO	Chinese hamster ovary cells
C _{max}	maximum observed concentration
COVID-19	coronavirus disease of 2019
DNA	deoxyribonucleic acid
EC ₅₀	the concentration that gives-half maximal response
ECG	electrocardiogram
ECP	eosinophil cationic protein
EDN	eosinophil-derived neurotoxin
eCRF	electronic case report form
E _{max}	maximum PD response

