5.7.4.1.2 Adverse Event Reporting

The recording of AEs will begin after the subject signs the informed consent form and will continue until discharge (or early termination). All AEs, whether serious or nonserious and whether or not related to the study drug, must be recorded in the eCRF. Study subjects will be instructed to warn study staff if he or she has any unexpected symptoms. In addition, all subjects will receive a reminder telephone call approximately 24 hours before Check-in.

Any SAE (whether expected or unexpected) must be entered into the eCRF system and reported by facsimile to the medical monitor or designee using the SAE Reporting Form within 24 hours of the investigator or study clinic staff becoming aware of the event. It is the responsibility of the investigator to report all SAEs to the medical monitor, to provide the most complete report possible, and to assess each SAE for its relationship to the study drug. The investigator is responsible for obtaining follow-up information on all SAEs and submitting follow-up SAE data. Any unexpected SAEs must be reported promptly to the investigator's IRB as per the IRB's requirements.

In the event of a fatal or life-threatening SAE, the sponsor will notify the appropriate FDA authorities by telephone or facsimile within 7 calendar days of receipt of the report. The sponsor will follow all 7-day alert reports with a written report within 10 working days of receipt of the case. Serious AE cases that concern nonfatal, nonlife-threatening events that are unexpected and at least possibly related to the study drug will be submitted in writing to the FDA within 10 working days of receipt.

Furthermore, any AEs that are not expected, occur at a higher frequency, or would require modification of the study protocol and/or informed consent must be reported to the FDA within 10 working days.

Adverse events that are assessed by the investigator as possibly or probably related to the study drug will be followed until they resolve or stabilize. All SAEs will be followed until resolution.

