5.9.8 Safety Analyses

5.9.8.1 Adverse Events

All AEs will be coded using the latest version of the Medical Dictionary for Regulatory Activities. The incidence of TEAEs, organized by system organ class and frequency, will be summarized by seriousness, severity, relationship to treatment, and by treatment at onset of the TEAE. A detailed listing of serious AEs and TEAEs leading to withdrawal will also be provided.

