7.7. Safety Analyses

7.7.1 Adverse Events

All AEs will be coded using the latest version of the Medical Dictionary for Regulatory Activities (MedDRA). The incidence of TEAEs, organized by system organ class and frequency, will be summarized by seriousness, severity, relationship to treatment, and by treatment at onset of the TEAE. A detailed listing of serious AEs and TEAEs leading to withdrawal will also be provided.

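### The TEAE definition tests only onset after dosing, so an AE already open at dosing that worsens afterwards can be left out of the TEAE incidence tables

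*Protocol*

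**What the plan says.** Protocol 5.7.4.1.1 gives three relevant statements.

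- An AE is an unwanted finding or illness linked in time to study drug use, whatever its cause.
- "Events or conditions that increase in frequency or severity during or as a consequence of use of a drug in human clinical trials" also count as AEs.
- "A treatment-emergent adverse event (TEAE) is defined as an AE that begins after study drug administration".

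Protocol 5.7.4.1.2 sets the recording window: "The recording of AEs will begin after the subject signs the informed consent form and will continue until discharge (or early termination"). Screening runs from Day -21 to Day -2 and check-in is Day -1. AE monitoring is listed at both visits (5.6.2 and 5.6.3.1).

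On analysis, Protocol 5.9.8.1 states: "The incidence of TEAEs, organized by system organ class and frequency, will be summarized by seriousness, severity, relationship to treatment", and also by treatment at TEAE onset. SAP 7.7.1 repeats this: "The incidence of TEAEs, organized by system organ class and frequency, will be summarized" by the same breakdowns. The SAP does not define a TEAE. The safety paragraph of the protocol synopsis is broader: "The incidence of AEs, organized by system organ class and preferred term, will be summarized with a focus on treatment-emergent AEs".

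Both documents put all data into listings (Protocol 5.9.3, SAP section 7). Serious AEs are listed without a restriction to TEAEs.

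**The concern.** The AE definition and the TEAE definition do not match. The first recognises worsening; the second looks only at when the event began. An event that opens between consent and dosing and becomes more severe or more frequent after dosing is the case where they part.

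Such a case is plausible in this design. Abnormal physical examination findings are recorded as AEs (Protocol 5.9.8.5), and comprehensive examinations take place before dosing. Inclusion criterion 3 admits subjects with abnormal findings judged not clinically significant. Caffeine is stopped for 48 hours before dosing (5.8.9), and headache is among the common mepolizumab reactions listed in 5.1.3. A hypothetical mild headache that starts on Day -1 and becomes severe after dosing would be the kind of event a safety table should show.

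What is at stake is whether TEAE incidence and severity by arm capture aggravation after dosing as well as new onset.

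**Working it through.** The documents state no figure to reproduce, so the check is mainly a comparison of texts.

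**Step 1. Can an AE be on record before dosing?** Yes. "The recording of AEs will begin after the subject signs the informed consent form", and dosing is on Day 1, so recording can start up to 21 days earlier.

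**Step 2. Is worsening after dosing an AE?** Yes, by the second statement in 5.7.4.1.1.

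**Step 3. Is that worsening a TEAE?** The only test is whether the AE begins after dosing. Two recording conventions give two answers:

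| How the worsening is recorded | Onset date | TEAE? |
|---|---|---|
| New AE entry | After dosing | Yes |
| Change of grade on the existing entry | Before dosing | No |

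Neither document chooses between them.

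**Step 4. Where would the second case appear?**

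| Output | Included? |
|---|---|
| TEAE incidence, Protocol 5.9.8.1 | No |
| TEAE incidence, SAP 7.7.1 | No |
| AE incidence as planned in the synopsis | Yes, if all AEs are tabulated |
| Listing of TEAEs leading to withdrawal | No |
| Listing of serious AEs | Only if serious |
| General data listings | Yes |

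**Step 5. Does onset matter elsewhere?** Yes. All four causality categories in 5.7.4.1.4 are framed by the timing of AE onset relative to study drug. If the pre-dose onset date is kept, the relationship would be graded against a date before any drug was given.

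**Step 6. Size.** Inputs: 8 subjects per arm and 9 arms (SAP 3.1, Table 1).

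- One subject in one arm: 1/8 = 12.5 percentage points. For example, 2/8 = 25% would be reported as 1/8 = 12.5%.
- The same subject over the whole study: 1/72 = 1.4 percentage points.

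The 12.5-point change applies to the table row for that event. The row for any TEAE changes only if the subject has no other TEAE. The documents give neither the frequency of AEs open at dosing nor the proportion that worsen, so no expected number of omitted subjects can be derived.

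**The case against.** The strongest reply is that the sentence on increasing frequency or severity, placed just before the TEAE definition, already makes the worsening an AE in its own right. That AE begins after dosing and is a TEAE. The reading is fair, and it means exclusion is not established. It is not required by the text, however: the sentence says what counts as an AE and is silent on onset date and on opening a new record. The rule may be in the data management plan, where Protocol 7.4 places the detail of data collection. That plan is not among the documents reviewed, and the definition itself should not depend on it.

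A reader might infer that the event is lost from every AE incidence table. The documents do not support that, because the synopsis plans incidence of AEs with TEAEs as the focus, not the limit. The synopsis therefore differs from 5.9.8.1 and SAP 7.7.1, which is a separate reason to reconcile them.

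A reader might also infer a known downward bias or a count of missed subjects. Neither follows. No rate is given, the subjects are healthy and are rechecked for eligibility on Day -1, and the same definition applies to every arm including placebo, so no distortion of between-arm comparisons has been shown.

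Finally, the primary endpoints are eosinophil measures, safety is summarised descriptively, and the event stays visible in listings. That limits the severity. Listings do not replace incidence tables, so the case for a clarification stands.

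**Conclusion.** The point holds as a gap in the definition with a possible consequence. The onset-only wording can leave a pre-dose AE that worsens after dosing out of the TEAE tables in Protocol 5.9.8.1 and SAP 7.7.1. This depends on one condition that the documents leave open: that the event keeps its pre-dose onset date.

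Where it happens, one subject shifts the incidence of that event in an arm of 8 by 12.5 percentage points. How often it would happen is unknown.

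Severity is minor. The primary PD analysis is untouched, and the data remain in the listings.

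**What to change.** 1. In Protocol 5.7.4.1.1, define a TEAE as an AE that begins, or increases in severity or frequency, after administration of study drug or placebo. Refer to this definition in SAP 7.7.1.
2. In the eCRF completion instructions, state that worsening after dosing is entered as a new AE with its own onset date, so that severity and relationship are graded on the post-dose event.
3. Align the AE summary in the synopsis with Protocol 5.9.8.1 and SAP 7.7.1, so that all three say whether incidence is tabulated for all AEs or for TEAEs only.

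The cost is one sentence in the protocol, a cross-reference in the SAP, one eCRF instruction and one edit to the synopsis. Reported TEAE counts may be slightly higher. Design, sample size and endpoints do not change.

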5.7.4.1.2 Adverse Event Reporting

The recording of AEs will begin after the subject signs the informed consent form and will continue until discharge (or early termination). All AEs, whether serious or nonserious and whether or not related to the study drug, must be recorded in the eCRF. Study subjects will be instructed to warn study staff if he or she has any unexpected symptoms. In addition, all subjects will receive a reminder telephone call approximately 24 hours before Check-in.

Any SAE (whether expected or unexpected) must be entered into the eCRF system and reported by facsimile to the medical monitor or designee using the SAE Reporting Form within 24 hours of the investigator or study clinic staff becoming aware of the event. It is the responsibility of the investigator to report all SAEs to the medical monitor, to provide the most complete report possible, and to assess each SAE for its relationship to the study drug. The investigator is responsible for obtaining follow-up information on all SAEs and submitting follow-up SAE data. Any unexpected SAEs must be reported promptly to the investigator's IRB as per the IRB's requirements.

In the event of a fatal or life-threatening SAE, the sponsor will notify the appropriate FDA authorities by telephone or facsimile within 7 calendar days of receipt of the report. The sponsor will follow all 7-day alert reports with a written report within 10 working days of receipt of the case. Serious AE cases that concern nonfatal, nonlife-threatening events that are unexpected and at least possibly related to the study drug will be submitted in writing to the FDA within 10 working days of receipt.

Furthermore, any AEs that are not expected, occur at a higher frequency, or would require modification of the study protocol and/or informed consent must be reported to the FDA within 10 working days.

Adverse events that are assessed by the investigator as possibly or probably related to the study drug will be followed until they resolve or stabilize. All SAEs will be followed until resolution.

5.7.4.1.3 Assessment of Severity

The investigator will assess the severity of each AE using the following scale:

- Mild: The subject is aware of the AE but is still able to perform all activities; minimal or no medical intervention or therapy is required.
- Moderate: The subject has to discontinue some activities due to the AE; minimal or no medical intervention or therapy is required.
- Severe: The subject is incapacitated by the AE and is unable to perform normal activities; significant medical intervention or therapy is required, and hospitalization is possible.

